8.2.4. Adverse Event Safety Analyses

Adverse events will be coded using the Medical Dictionary for Regulatory Activities (MedDRA) coding dictionary.

The reporting of the CEC-adjudicated CV endpoint events has been described in Section 7.2, Section 8.2.1, and Section 8.2.2. However, AE summaries and analysis will also include the AEs and SAEs associated with the adjudicated events listed below:

- All-cause mortality (CV and non-CV mortality)
- Non-fatal MI
- Non-fatal stroke
- Hospitalization for HF
- Thromboembolic events (vascular access thrombosis, deep vein thrombosis, pulmonary embolism)

200807 | Statistical Analysis Plan Amendment 3 03 Mar 2021 | TMF-11879471 | 2.0

CONFIDENTIAL

200807

For the purpose of AE summaries and analysis, the investigator-reported AE details will be used, regardless of the adjudication outcome of the event.

Adopting recommendations from the Pharmaceutical Research and Manufacturers of America (PhRMA) Safety Planning, Evaluation and Reporting Team (SPERT) [Crowe, 2009], the first two tiers of the three-tier system will be used for the evaluation of AEs to examine the level of statistical evidence for differences between treatment groups.

- Tier 1 events in this study are defined as treatment emergent AEs of special interest (AESI). Tier 1 events will include AEs which meet criteria for inclusion as an AESI (see Section 10.6.4). Statistical comparisons will be made to compare the number and % of AESIs between the treatment groups, using the CMH chi-square test. A nominal statistical association will be declared if the unadjusted two-sided p-value for an event is less than 0.05.
- Tier 2 events in this study are defined as the most common treatment emergent AEs (those occurring in ≥ 5% of subjects in any treatment group). Tier 2 events are mutually exclusive of the Tier 1 AESI events. Any statistical comparisons for Tier 2 events will be made to compare treatment groups with multiplicity adjustment, using a CMH chi-square test, and the double false discovery rate (FDR, see Section 10.6.4) [Mehrota, 2012]. The double FDR multiplicity procedure is designed to limit the number of false positive signals identified to no more than two-sided 10% (the false discovery rate).

Unless otherwise specified, all other AE and SAE summaries will include all AEs.

See Section 10.4.1 for AE treatment state definitions.

The adverse event safety analyses will be based on the Safety population, unless otherwise specified.

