8.2.4.2. Planned Adverse Event Safety Statistical Analyses

AESIs & PhRMA SPERT Adverse Event Analyses

Adverse events of special interest are described in Section 10.6.4.

Summaries of AESIs will include the number, percentage and rate per 100 person-years of subjects having at least one occurrence, the number of events, the number of subjects by number of occurrence, the characteristics of the AE (serious, drug-related, etc.), outcome, maximum intensity, time to first onset/worsening, and action taken summarized by treatment group. For each count, a subject will be summarized as follows:

- Serious/drug-related/severe/fatal: If any specific AE falls in the respective category, the subject will be counted in that category.
- Outcome: The subject will be counted within a category if there is at least one specific AE in that category.
- Maximum intensity: The specific AE with the maximum intensity will be counted for this purpose. For example, a subject will be counted in the 'severe' category if there is at least one specific AE with severe intensity. A subject will be counted in the 'moderate' category if there is at least one specific AE with moderate intensity and there is no specific AE with severe intensity.
- Time to first onset/worsening (days): The earliest of onset dates for the specific AE treatment start + 1

If the AE onset date/AE worsening and/or resolution date is missing or incomplete in the database for any occurrence of the specific AE, time to first onset/worsening will be left missing for the subject. These summaries of special interest AEs will be provided for those AEs classified as treatment emergent.

Cumulative incidence function (CIF) plots may be produced for each AESI summarizing the time to first occurrence of the AESI by treatment group. If there are less than 20 subjects total for both the daprodustat and rhEPO arm, then these plots will not be created. Competing risks for the AESI cumulative incidence plots include:

AE of Special Interest (Event of interest)	Competing Risk Events
Thrombosis and/or tissue ischemia secondary	Death due to any cause prior to the AESI
to excessive erythropoiesis	
Cardiomyopathy	Death due to any cause prior to the AESI
Pulmonary artery hypertension	Death due to any cause prior to the AESI
Cancer-related mortality and tumor progression	All other non-cancer-related death prior to the
and recurrence	AESI (use death date as the competing risk
	date)

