10.2.1.3. Schedule of Assessments for Subjects Permanently Discontinuing Randomized Treatment

Protocol Activity All assessments pre-dialysis unless otherwise specified	Early Treatment Discontinuation	Day 1 through Week 52 ⁷			
(Note: All visit timings are relative to Day 1)	Visit (within 2 weeks of discontinuing randomized treatment)	Week 4, 16, 28, 40, 52 ± 2 weeks	Unscheduled		
IRT system transaction	Х				
SBP/DBP, HR (pre- and post-dialysis for in-center HD subjects; between treatments for HHD; at study visits per standard of care for PD) (single readings unless otherwise indicated)	X (triplicate)	x	Х		
ECG	Х				
Iron therapy, transfusions ¹	Х	Х	Х		
Serum pregnancy test (FRP only)	Xe				
HemoCue Hgb	Х	Х	Х		
Hematology ³ ,	Х	Х			
Clinical chemistry ³	Х	Х			
Ferritin, total iron, UIBC, hepcidin, lipids, iPTH	Х				
Hospitalization ¹ , kidney transplant ¹	Х	Х	Х		
Non-serious AEs, AEs of special interest, SAEs, clinical events	Х	Х	Х		
Review concomitant medications	Х	Х	Х		
Healthcare resource utilization (subject reported)	Х				
PGI-S, PGI-C ^{4, 9}	Х				
SF-36 ^{4, 9}	Х				
EQ-5D-5L& EQ-VAS ^{4, 5, 9}	Х				
ABPM sub-study (Appendix 12): 24 hour ABPM		X (Week 16)			
Record awake and sleep times		X (Week 16) ²			

Note: see footnotes on next page

200807

Schedule of Assessments for Subjects Permanently Discontinuing Randomized Treatment (Continued)

Protocol activity (visits ± 2 week)		Yea	r 2 7			Yea	r 3 ⁷				Year 47				
(Note: All visit timings are relative to Day 1)	Week 64	Week 76	Week 88	Week 100	Week 112	Week 124	Week 136	Week 148	Week 160	Week 172	Week 184	Week 196	Week 208	Unscheduled	End of Study ⁸
IRT system call															Х
SBP/DBP, HR (pre- and post- dialysis for in-center HD subjects, between treatments for HHD and PD subjects) (single readings unless otherwise indicated)	х	х	х	х	х	х	х	х	х	х	х	х	х	х	Х
HemoCue Hgb	Х	Х	Х	Х	Х	Х	Х	Х	Х	Х	Х	Х	Х	Х	
Hematology ³	Х	Hgb only	Х	Hgb only	Х	Hgb only	Х	Hgb only	Х	Hgb only	Х	Hgb only	Х		Х
Clinical chemistry ³	Х		Х		Х		Х		Х		Х		Х		Х
Hospitalization ¹ , kidney transplant ¹	Х	Х	Х	Х	Х	Х	Х	Х	Х	Х	Х	Х	Х	Х	Х
Non-serious AEs, SAEs, AEs of special interest, clinical events	Х	Х	Х	Х	Х	Х	Х	Х	Х	Х	Х	Х	Х	Х	Х
Review concomitant medications	Х	Х	Х	Х	Х	Х	Х	Х	Х	Х	Х	Х	Х	Х	Х

1. Record in eCRF, if applicable.

2. Subject will record sleep and wake time during the ABPM session.

3. See details on hematology and clinical chemistry in Protocol Section 7.4.11.

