10.4.1.4. Treatment States for AE Data

Non-serious AEs and serious AEs are to be recorded on the eCRF starting at the placebo run-in phase. Serious AEs assessed as related to study procedures or related to a GSK concomitant medication are to be recorded on the eCRF from the time a subject consents

200807

to participation in the study. AE of worsening of an on-going event will be counted once in a particular treatment state.

Treatment State	Definition
Pre-treatment	 For subjects with a non-missing screen failure date, if AE onset is on or before the screen failure date: AE Start Date ≤ Screen Failure Date For randomized subjects with a missing treatment start date, all AEs are considered pre-treatment For randomized subjects with a non-missing treatment start date, if AE onset date is before treatment start date: AE Start Date < Treatment Start Date
Placebo Run-In	If AE onset date or AE worsening date is on or after placebo run-in treatment start date & on or before placebo run-in treatment stop date: Placebo Run-in Treatment Start Date \leq AE Start Date \leq Placebo Run-in Treatment Stop Date Placebo Run-in Treatment Start Date \leq AE Worsening Date \leq Placebo Run-in Treatment Stop Date AE worsening during placebo run-in will be defined relative to the maximum intensity of AE prior to placebo run-in start date. AE worsening date is the first date in the placebo run-in period, when AE intensity increased relative to the maximum intensity of the AE prior to placebo run-in start date.
Post- randomization	If AE onset date or AE worsening date is on or after the randomization date Randomization date ≤ AE Start Date Randomization date ≤ AE Worsening Date AE worsening during post-randomization will be defined relative to the maximum intensity of AE prior to randomization date. AE worsening date is the first date in the post-randomization period, when AE intensity
Treatment emergent	increased relative to the maximum intensity of the AE prior to randomization date. If AE onset date or AE worsening date is on or after treatment start date & on or before the last non-zero dose date plus 1 day. Treatment Start Date ≤ AE Start Date ≤ Last Non-Zero Dose Date + 1 day Treatment Start Date ≤ AE Worsening Date ≤ Last Non-Zero Dose Date + 1 day AE worsening during treatment emergent will be defined relative to the maximum intensity of AE prior to randomized treatment start date.

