10.6.4.3. Adverse Events

Adverse Events

AEs of Special Interest

Adverse events of special interest are classified as follows:

- Thrombosis and/or tissue ischemia secondary to excessive erythropoiesis
- Cardiomyopathy
- Pulmonary artery hypertension
- Cancer-related mortality and tumor progression and recurrence
- Esophageal and gastric erosions
- Proliferative retinopathy, macular edema, choroidal neovascularization
- Exacerbation of rheumatoid arthritis
- Worsening of hypertension

Potential AESIs will be identified through a pre-defined terms of interest process in which predefined lists of AE preferred terms corresponding with each AESI will be used to identify events considered to be potential AESIs. Sites will be prompted via query to complete any necessary additional information for these AESIs in the eCRF.

For the category of thrombosis and/or tissue ischemia secondary to excessive erythropoiesis, after the terms of interest list has been applied, the additional Hgb criteria described below will be applied to identify only those events that are considered to be secondary to excessive erythropoiesis as meeting the AESI definition for thrombosis and/or tissue ischemia secondary to excessive erythropoiesis.

Thrombosis and tissue ischemia events will be considered to be secondary to excessive erythropoiesis if during the window of [AE start date – 30 days, AE start date +15 days] any one of the following 3 events occurs:

- Any Hgb value \geq 13 g/dL (measured pre-dialysis)
- Hgb increase > 2 g/dL over 2 weeks (+1 week)
 - Note: for programming purposes, a +1 week window is applied, corresponding to the allowable visit window, to look for increases > 2 g/dL over 3 weeks
- Hgb increase > 4 g/dL over 4 weeks (+1 week)
 - Note: for programming purposes, a +1 week window is applied, corresponding to the allowable visit window, to look for increases > 4 g/dL over 5 weeks

To identify Hgb increases that meet the increase criterion above, all Hgb values taken within [AE start date – 58 days, AE start date + 15 days] will be identified. This corresponds to identifying Hgb

200807

Adverse Events

values that occurred 4 weeks before the [AE start date – 30 days, AE start date +15 days] window of interest. HemoCue Hgb and central laboratory Hgb values will then be evaluated separately to identify increases, so that HemoCue and central laboratory Hgb values are not compared to each other to identify an increase.

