 Post-Randomization last contact date for censoring (subjects not having AE) will be defined as the study completion date. 	
 Treatment emergent last contact date for censoring (subjects not having AE) will be defined as follows: 	
 1 day after the last non-zero dose date (last non-zero dose date + 1) for subjects not having treatment emergent AE and continuing on study past (last non-zero dose date + 1) 	
 Last non-zero dose date for all other subjects 	
AE Patient Years: (Cumulative total of time to AE for subjects who have the AE +	

200807

Advers	se Events
	Cumulative total of censoring time for subjects without the AE) / 365.25
	 For treatment emergent AEs, the start date of the patient years value for each subject should be the treatment start date.
	 For post-randomization AEs, the start date of the patient years value for each subject should be the randomization date.
	 For follow-up AEs, the start date of the patient years value for each subject should be 2 days after the last non-zero dose date (last non-zero dose date + 2).
•	Incidence Rate (per 100 patient years): (100 * Number of subjects with at least 1 AE) / AE person years
٠	For the analysis of the time to AE onset/worsening, if the AE onset/worsening date is missing then the time to AE onset/worsening will be counted as 1 day.
10.6.4	.4. Laboratory Parameters

Laboratory Parameters

•	If a laboratory value which is expected to have a numeric value for summary purposes, has a non-detectable level reported in the database, where the numeric value is missing, but typically a character value starting with ' <x' '="" or="">x' (or indicated as less than x or greater than x in the comment field) is present, the number of significant digits in the observed values will be used to determine how much to add or subtract in order to impute the corresponding numeric value. • Example 1: 2 Significant Digits = '< x' becomes $x - 0.01$ • Example 2: 1 Significant Digit = '> x' becomes $x + 0.1$ • Example 3: 0 Significant Digits = '< x' becomes $x - 1$</x'>
•	If there is more than one laboratory value on the same date for the same laboratory test, then the laboratory values associated with scheduled visits will be used. Hgb summaries and analyses are an exception and should use the data handling conventions outlined in Section 10.6.3.

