10.7. Appendix 7: Premature Withdrawals & Handling of Missing Data

10.7.1. Premature Withdrawals

Element	Reporting Detail
General	 Subject study completion (i.e. as specified in the protocol) was defined as completing all phases of the study including the End of Study visit, with the following exception: subjects who die while on study are also considered as having completed the study. Withdrawn subjects will not be replaced in the study. All available data from subjects who were withdrawn from the study will be listed and all available planned data will be included in summary tables and figures, unless otherwise specified. Per protocol, subjects may prematurely discontinue study drug but are encouraged to remain in the study.

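### No named between-arm AESI analysis counts a malignancy with onset or worsening later than one day after the last dose, although AESIs are collected to End of Study

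*SAP*

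**What the plan says.** Section 10.6.4.3 lists eight AESI categories. One is "Cancer-related mortality and tumor progression and recurrence", and it has no window of its own.

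Two statements set the window for AESI analysis. Section 8.2.4.2 says of the descriptive AESI tables: "These summaries of special interest AEs will be provided for those AEs classified as treatment emergent". Section 8.2.4 sets the scope of the formal comparison: "Tier 1 events in this study are defined as treatment emergent AEs of special interest (AESI"). Tier 1 gives the relative risk, its 95% confidence interval and a two-sided p-value.

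Section 10.4.1.4 defines treatment emergent by onset as "Treatment Start Date ≤ AE Start Date ≤ Last Non-Zero Dose Date + 1 day", with a matching rule for worsening. It also defines a post-randomization state, "Randomization date ≤ AE Start Date", which has no upper limit, and a follow-up state for events after the treatment-emergent window. Section 10.6.4.3 supplies person-time for these states: "For post-randomization AEs, the start date of the patient years value for each subject should be the randomization date".

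On collection, section 10.7.1 says: "Per protocol, subjects may prematurely discontinue study drug but are encouraged to remain in the study". The schedule for such subjects in 10.2.1.3 has the row "Non-serious AEs, SAEs, AEs of special interest, clinical events", marked at every scheduled visit from Week 64 to Week 208 and at End of Study. The year 1 table has an equivalent row.

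**The concern.** A window that closes a day after the last dose suits harms that appear and resolve with exposure. For malignancy, the recorded date need not fall in that window. A tumor worked up because of symptoms that led the subject to stop, with onset recorded two days after the last dose, is outside every AESI analysis that states a window. So is a recurrence a year later, although the site is asked to report it.

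The window follows the last dose physically taken. Section 10.6.1 notes that a subject can complete the study while on a zero dose under the algorithm, so the window can close while the subject is still being managed within the trial.

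The trial is open-label. If the timing of or reasons for stopping differ by arm, a comparison restricted to on-treatment time no longer rests wholly on randomization. For cardiovascular harm the SAP provides for this: MACE is analysed in all randomized subjects over follow-up, and the on-treatment version is supportive, with a tail of 28 days. The cancer AESI has a one-day tail and no all-follow-up counterpart.

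**Working it through.** **Which displays can contain a malignancy that starts or worsens after last non-zero dose + 1 day?**

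| SAP display | Window stated | Includes it? |
|---|---|---|
| AESI summaries (8.2.4.2) | treatment emergent | no |
| Tier 1 relative risk, CI, p-value (8.2.4, 8.2.4.2) | treatment emergent | no |
| General AE tables (8.2.4.2) | pre-treatment or treatment emergent | no |
| SAE tables (8.2.4.2) | treatment emergent | no |
| AESI cumulative incidence plots (8.2.4.2) | none stated; optional; no test | unclear |
| AE listing (8.2.4.2) | none stated | yes, but not a comparison |
| MACE and all-cause mortality (7.2.2, 8.2.2.2, 10.6.4.1) | all randomized follow-up / vital-status period | fatal cases, as deaths |
| Cause-of-death summary (8.2.2.2) | follows all-cause mortality | fatal cases, by cause |

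The rows that clearly reach past the last dose are a listing and analyses of death. A non-fatal tumor after stopping appears in no named comparison.

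**Are the needed definitions present?** Yes. The post-randomization state is in 10.4.1.4, and its censoring date and person-years are in 10.6.4.3. No display in 8.2.4 refers to it.

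**Size.** The SAP gives no discontinuation rate, follow-up distribution or cancer rate, so there is no stated figure to reproduce. The following is illustration only. Assume a constant discontinuation hazard h, potential follow-up T = 2.5 years, and no deaths or withdrawals.

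Mean time on treatment = (1 − e^(−hT)) / h

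- h = 0.2: (1 − e^(−0.5)) / 0.2 = 1.97 years; share off treatment = 1 − 1.97/2.5 = 21%
- h = 0.4: (1 − e^(−1)) / 0.4 = 1.58 years; share off treatment = 1 − 1.58/2.5 = 37%

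These are shares of follow-up time. They become shares of malignancies only if the cancer hazard is also assumed constant on and off treatment.

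**The case against.** Treatment-emergent reporting is a conventional choice. The SAP states no latency or risk window for cancer, so it cannot be cited for the view that the harm is delayed. That is fair. The point does not depend on latency: it rests on events that are collected and then left out of every named comparison.

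A reader might infer that malignancy after stopping is compared nowhere at all. The SAP does not support that. Fatal cases count in the ITT MACE analysis and in all-cause mortality, and the cause-of-death summary can show them. Cancer mortality is part of this AESI, so this limit on the point is material.

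A reader might also infer that every AESI display is restricted. The sentence about treatment-emergent events refers to the summaries before it. The cumulative incidence plots come after it, name no window, and give cancer its own competing-risk rule. They may be produced or not, carry no test, and are dropped when fewer than 20 subjects are involved. They leave the matter unclear without filling the gap.

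Section 8.2.4 says that all other AE and SAE summaries include all AEs unless specified otherwise. It follows the Tier 1 and Tier 2 definitions and concerns other summaries, so it does not widen the AESI window. The unused person-time rules could mean that displays were intended and not named. If so, they should be named.

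The IDMC's periodic SAE reports (3.1) state no treatment-state limit, but they are interim monitoring, not a final comparison.

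The strongest objection is to letting an all-follow-up analysis lead. Subjects off randomized treatment may receive non-randomized ESA, so daprodustat subjects may move to the comparator's class, and dilution toward no difference is not cautious for a harm. This stands as a reason to add the analysis beside the existing one.

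**Conclusion.** The point holds in this form: the SAP names no between-arm AESI analysis that includes a malignancy with onset or worsening after last non-zero dose + 1 day. Fatal cases are captured only as deaths. Non-fatal new, progressing or recurrent tumors after stopping are compared in no named analysis, although they are collected to End of Study and the SAP already defines the state and person-years needed.

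The size is unknown from the document. The 21% to 37% rests wholly on the assumed hazard and follow-up. It should not be read as a proportion of cancers missed or as a bias of known direction. It is a gap in safety reporting that should be closed, and it does not affect the co-primary conclusions.

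**What to change.** In 8.2.4.2, keep the treatment-emergent AESI analysis and add a post-randomization analysis for the cancer AESI, from randomization to study completion or withdrawal, by randomized arm. Report for each arm the count and rate per 100 person-years, the relative risk with 95% CI, and a cumulative incidence plot with non-cancer death as the competing event. Use the state in 10.4.1.4 and the person-year rules in 10.6.4.3, and show the two versions side by side.

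Two wording details need settling. Section 8.2.4 defaults to the Safety population, so name the ITT population for this display. The post-randomization censoring rule in 10.6.4.3 mentions only the study completion date, so state that withdrawn subjects are censored at the withdrawal date defined in 10.6.1. Also state the window for the optional AESI cumulative incidence plots.

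The cost is SAP wording, one table and one figure. No new data are needed. The downside is that off-treatment time, including time on non-randomized ESA, dilutes an on-drug effect; the retained treatment-emergent version covers this.

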8.2.5. Clinical Laboratory Safety Analyses

Clinical chemistry, hematology and other laboratory tests are assessed in this study according to the schedule outlined in the Time and Events table (see Section 10.2.1). The following tests will be summarized in clinical laboratory displays:

	Potassium (serum)	Aspartate aminotransferase (AST)	Albumin
Clinical Chemistry	Calcium (albumin corrected)	Alanine amintotransferase (ALT)	Blood Urea Nitrogen (BUN)
	Phosphate	Bilirubin (total and direct/indirect)	

	Platelet count	RBC indices:	Leukocyte (white blood cell) count with Differential		
	Erythrocyte (red blood cell) count	Mean corpuscular volume (MCV)	Neutrophils (absolute and segmented)		
	Reticulocyte count	Mean corpuscular hemoglobin (MCH)	Lymphocytes		
	Hematocrit	Mean corpuscular hemoglobin concentration (MCHC)	Monocytes		
		Erythrocytes (red cell) distribution width (RDW)	Eosinophils		
			Basophils		

200807

Other laboratory tests	Intact parathyroid hormone (iPTH)	Hemoglobin A1c (HbA1c) in diabetic subjects	High-sensitivity C-reactive protein (hs-CRP)	
------------------------------	--------------------------------------	--	--	--

Summaries of central laboratory Hgb values, HemoCue Hgb values, iron parameter values (serum iron, ferritin, hepcidin, TIBC, TSAT), and lipid parameter values (total cholesterol, direct LDL-C, HDL-C) are included in earlier efficacy and safety sections and will not be included with clinical laboratory displays. However, these parameters may be included in PCI summaries.

The clinical chemistry tests performed in this study include ALT, AST and bilirubin. In addition to being summarized with the clinical chemistry values, these laboratory values will be included in some of the Hepatobiliary (liver) displays.

In addition to the visits listed for the laboratory assessments in the Time and Events table (see Section 10.2.1), any of these assessments can be performed at an unscheduled/retest visit or at the follow-up visit at the discretion of the investigator. See Section 10.5.3 for handling of unscheduled values. The laboratory's normal range values will be provided by the central laboratory and potential clinical importance thresholds are defined in Section 10.8.1.

All of the tabular summaries described below will include summaries in SI units; conventional units will also be provided for the following laboratory tests: MCHC, albumin corrected calcium, phosphate, albumin, BUN, total cholesterol, LDL-C, and HDL-C. Conversions from SI units to conventional units are included in Section 10.6.4. Hemoglobin summaries will only use conventional mg/dL units. Summaries of reticulocytes will be provided for the total count and percent of total erythrocytes and summaries of neutrophils, lymphocytes, monocytes, eosinophils, and basophils will be provided for total counts and differentials (percent of total leukocytes).

The clinical laboratory safety analyses will be based on the Safety population, unless otherwise specified.

